## 7.2 Exclusion Criteria

- 1. Discontinuation of enzalutamide or abiraterone less than 3 weeks prior to the start of study medication.
- 2. Prior chemotherapy and experimental therapy (PARP or checkpoint inhibitor).
- 3. Ongoing acute treatment-related toxicity associated with a previous therapy greater than grade 1 except for grade 2 alopecia or neuropathy.
- 4. History of impaired adrenal gland function (e.g., Addison's disease, Cushing's syndrome).
- 5. Known gastrointestinal disease or condition that affects the absorption of GT0918.
- 6. History of congestive heart failure New York Heart Association (NYHA) class III or IV or uncontrolled hypertension at screening.

7. History or family history of long QT syndrome, or ECG corrected QT interval equal to and over 500 ms (CTCAE grade 2) at baseline.
8. History of other malignancy within the previous 3 years, except basal cell or squamous cell carcinoma, or non-muscle invasive bladder cancer.
9. Use of systemic glucocorticoid (e.g., prednisone, dexamethasone) within 14 days prior to the start of study medication. Inhaled or topical steroids are allowed.
10. Co-administration of CYP3A4 ligands that serve as substrates or induce or inhibit the enzyme. (See Appendix 4 of list of medications) If such medication needs to be used for the chronic illness, the medication shall be changed to another one that is not on the list or the dose should be reduced, at the discretion of the Investigator.
11. Prior use of any herbal products known to decrease PSA levels (e.g., PC-SPES or saw palmetto) within 30 days prior to the start of study medication.
12. Major surgery within 30 days prior to the start of study medication.
13. Blood transfusion (including blood products) within 1 week of screening.
14. Serious persistent infection within 14 days prior to the start of study medication.
15. Serious concurrent medical condition including CNS disorders.
16. Previous history of difficulty swallowing capsules.
17. Known hypersensitivity to GT0918 or its excipients (See Appendix 5 for drug details).
18. Any condition that, in the opinion of the investigator, would impair the subject's ability to comply with study procedures

### 7.3 Withdrawal, Removal, and Replacement of Subjects

A subject may voluntarily withdraw or be withdrawn from the study at any time for reasons including, but not limited to, the following reasons. All sites are required to inform project team, Medical Monitor or/and sponsor and discuss possible alternatives in order to keep high quality of study data. No replacement of subjects in Phase II study.

- 1) Progressive disease
- 2) Unacceptable toxicity or AE
- 3) Subject withdrawal of consent: At any time, a subject's participation in the study may terminate at his request or on the basis of the Investigator's clinical judgment. The reason for subject withdrawal will be noted on the case report form (eCRF).
- 4) Intercurrent illness: a condition, injury, or disease unrelated to the primary diagnosis that became apparent during treatment and necessitated the subject's termination from the study.

Suzhou Kintor Pharmaceutical, Inc.  
Protocol#: GT0918-US-1002

Proxalutamide (GT0918)

- 5) General or specific changes in the subject's condition that renders him ineligible for further treatment according to the inclusion/exclusion criteria.
- 6) Protocol deviation: The subject's findings or conduct failed to meet the protocol entry criteria or the subject failed to adhere to the protocol requirements (e.g., drug noncompliance, failure to return for defined number of visits). The deviation necessitated premature termination from the study.
- 7) Lost to follow-up: The subject stopped coming for visits, and study personnel were unable to contact the subject after at least 3 documented attempts (including certified letter) to contact the subject.
- 8) This study may be terminated at the discretion of the Sponsor or any regulatory agency. An Investigator may elect to discontinue or stop the study at his or her site for any reason including safety or low enrollment.
- 9) There is no subject replacement in this phase II study.

#### **7.4 Follow-Up for Drug Discontinuation/Subject Withdrawal from Study**

If a subject discontinues study treatment and is withdrawn from the study for any reason, the study site must immediately notify the project team and sponsor and discuss possible alternatives in order to keep high quality of study data. The date and the reason for study discontinuation must be recorded on the eCRF. In the event where a subject discontinues prematurely from the study due to a study drug-related AE or SAE, the AE or SAE will be followed until it is resolved (returns to normal or baseline values) or stabilizes. Office visits are recommended for these subjects until it is judged by the investigator to be no longer necessitated.

Once a subject is withdrawn from the study, the subject may not re-enter the study.

## **8 TREATMENTS**

### **8.1 Details of Study Medication**

GT0918 is an androgen receptor antagonist (MW 517.5 g/mol). The dosage form for clinical research is a 100 mg tablet weighing 320 mg per tablet. The 100 mg tablet is circular in shape with 10 mm in diameter. The color is light pinky with PRO print on pills. The drug product tablets are packaged in PTP aluminum and PVC blister foils. These packaging materials are in compliance with 21CFR 174-186 – Indirect Food Additive Regulations.

Suzhou Kintor Pharmaceutical, Inc.  
Protocol#: GT0918-US-1002

Proxalutamide (GT0918)

The recommended storage conditions for GT0918 tablets are room temperature, with a shelf-life of 2 years. All drug supplies will be provided by the Sponsor.

## **8.2 Dosing Schedule (expanded/phase II)**

In expanded/Phase II, all subjects will be randomized into 2 groups to take either 400 or 500mg oral GT0918 once a day for 28 days each cycle for initial treatment of 6 cycles. At the end of 6/12/18/24 cycles of GT0918 treatment, subjects without progressive disease (PD) may continue study drug GT0918 treatment with the approval of the investigator, medical monitor and sponsor; treatment can continue until a subject experience an intolerable adverse event (AE) or experiences disease progression, withdraws consent or until termination of the study by the sponsor. All subject's disease condition will be re-evaluated every 3 cycles (84 days  $\pm$  7) in order to qualify for additional treatment. If any subject shows mix response (for example, only PSA raising or mix response on imaging scan, or lesion increasing in size without PSA raising, or no clinical progression), treatment can be continued for additional 4-6 weeks and then another PSA or tumor assessment can be scheduled to confirm if disease progression is determined. In case PD is confirmed that will conclude with an end-of-study visit.

All subjects will have safety review at the end of every cycle conducted by participating principal investigators (PIs) and medical monitor. In addition, the medical monitor can prompt a safety review at any time.

Toxicity reported during the study will be graded according to the CTCAE (Common Terminology Criteria for Adverse Events) v4.03. Laboratory Assessments will include blood chemistry, hematology, ECGs, and urinalysis.

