(AEs), or withdrawn consent. Subjects will end the study by completing the end of study (EOS) visit/assessment. The safety follow-up visit will occur 30 days after the last dose. Any subject with drug related AE or SAE will be followed until resolution or the subject's condition stabilizes, which comes first. The safety follow-up visit can be performed via phone or in clinic as required.

Disease progression will be assessed by three methods as follow over the duration of the study.

- 1) Clinical assessment
- 2) Biochemical (PSA) progression measured every 4 weeks
- 3) Radiographic progression by CT scan and/or bone progression by radionuclide bone scan every 12 weeks

Progressive disease will be considered on the occurrence of the first assessed progression event. For subjects with PSA progression may continue on study drug until radiographic and/or clinical progression, at the discretion of the Investigator and with the Medical Monitor agreement. A treatment diagram for the study is provided below in **Figure 1**.

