**Duration of study (expanded/phase II):**

The part II study will have 3 periods, screening, treatment and post-treatment safety follow up. The screening period is up to 3 weeks. The treatment period includes first 6-cycle treatment and potential additional cycles for eligible subjects up to 24 cycles. After the first 6 cycles of treatment, subjects without progressive disease (PD) may continue GT0918 treatment with the approval of the investigator and sponsor; treatment can continue until a subject experience an intolerable adverse event (AE) or bone or radiographic disease progression, withdraws consent or termination of the study by the sponsor. This approval is required for entering the next 6 cycle treatments (for starting on C7D1, C13D1, C19D1, C25D1). All subjects will have End-of-study visit over 30 days after last dose. A post-treatment safety window of 30 days is allowed for record of any possible delayed study drug-related AEs and SAEs after the last dose of study medication.

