## 6 INVESTIGATIONAL PLANS (EXPANDED/PHASE II)

### 6.1 Description of Overall Study Design and Plan

This expanded/Phase II, open-label, randomized, and multi-center clinical study is designed to evaluate the safety, tolerability and efficacy of GT0918, an orally administered AR antagonist, in mHSPC or mCRPC subjects who failed prior treatment of either abiraterone or enzalutamide. All subjects will be randomized to either take 400 mg or 500 mg for daily administration as recommended by the phase I clinical data. Each arm will be 30 subjects. Subjects will have initial treatment up to 6 cycles with an option to continue up to additional 24 cycles as long as there is no progressive disease, no intolerable adverse event, no radiographic disease progression, no consent withdrawn by the subject or no termination of the study by the sponsor.

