### 6.2 Discussion of Study Design

GT0918 is an oral androgen receptor antagonist with superior characteristics compared to currently marketed AR antagonists based on both preclinical and clinical data.

Based on clinical experience and outcomes from phase 1 (part I) dose escalation of GT0918, it is recommended for 400 mg or 500 mg oral administration daily for the first initial treatment up to 6 cycles. Dose reduction is allowed for subjects (see Section 8.6.3) who experiences any study drug related intolerable toxicities. Study drug GT0918 is suggested to be taken on an empty stomach. If dosing before meal time, it is recommended to wait 1 hour before eating. If dosing after meals, it is recommended to wait 2 hours before taking the study drug.

Suzhou Kintor Pharmaceutical, Inc.  
Protocol#: GT0918-US-1002

Proxalutamide (GT0918)

By the end of 6 cycles of initial treatment, subjects will have an end-of-6-cycles assessment to be determined for further treatment (Section 9.2.2.) Eligible subjects (without PD) have the option to be treated for additional up to 24 cycles at their assigned dose level until PD, intolerable toxicity or as investigator's discretion (Section 9.2.3). At the end of 12, 18 and 24 cycles, assessments will be performed to determine if the subjects will move into the next 6 cycle treatment.

All subjects on study drug of GT0918 are required to perform End-of-Study (EoS) assessment before termination (Section 9.2.4). A post-treatment safety window of 30 days is allowed for any possible delayed study drug-related AEs and SAEs after the last dose of study medication or end-of-study visit which ever occur later. See schedule of assessments (Appendix 1)

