### **9.2.3 Expansion Study (Additional Cycles after Cycle 6 Day 28 (Cycle 7 Day 1, to Cycle 30 Day 28)**

Eligible subjects (no disease progression) have the option to continue additional cycles (up to 18 more cycles) on their assigned dose level until they exhibit PD and/or investigator discretion. Visits will occur every cycle/month, i.e. every 28 days (+/- 3 days). Every 3 cycles, the subjects will be given a disease assessment scan (CT and/or MRI or bone scan). Every 6 cycles, the subjects will be assessed by Investigator and discussed with Medical Monitor or/and Sponsor to determine whether to proceed into the next 6 cycles.

- Subject returns to office
- Disease Assessment scans (CT or MRI or bone scan) are to be performed every 3 cycles (84 +/- 14 days, Cycle 7 Day 1, Cycle 10 Day 1, Cycle 13 Day 1, Cycle 16 Day 1, Cycle 19 Day 1, Cycle 22 Day 1, Cycle 24 Day 28, Cycle 27 D28 and Cycle 30 D28).
- Vital signs
- Complete Physical Exam (Every 3 cycles on Cycle 7 Day 1, Cycle 10 Day 1 Cycle 13 Day 1, Cycle 16 Day 1, Cycle 19 Day 1, Cycle 22 Day 1, Cycle 24 Day 28, Cycle 27 D28 and Cycle 30 D28)
- Abbreviated Physical Exam (Cycle 8 Day 1, Cycle 9 Day 1, Cycle 11 Day 1, Cycle 12 Day 1, Cycle 14 Day 1, Cycle 15 Day 1, Cycle 17 Day 1, Cycle 18 Day 1, Cycle 20 Day 1, Cycle 21 Day 1, Cycle 23 Day 1, Cycle 24 Day 1, Cycle 26 Day 1, Cycle 27 Day 1, Cycle 29 Day 1, Cycle 30 Day 1)
- ECOG status
- Laboratory Tests: hematology, chemistry & electrolytes, testosterone, PSA, and urinalysis, lipid profile/blood glucose performed every 3 months (For subjects with abnormal lipid profiles monthly testing is required.)
- 12-lead ECG (every 3 cycles on Cycle 7 Day 1, Cycle 10 Day 1 Cycle 13 Day 1, Cycle 16 Day 1, Cycle 19 Day 1, Cycle 22 Day 1, Cycle 25 Day 1 and Cycle 28 Day 1 )

Suzhou Kintor Pharmaceutical, Inc.  
Protocol#: GT0918-US-1002

Proxalutamide (GT0918)

- Exploratory markers (every 3 cycles on Cycle 7 Day 1, Cycle 10 Day 1, Cycle 13 Day 1, Cycle 16 Day 1, Cycle 19 Day 1, Cycle 22 Day 1, Cycle 25 Day 1 and Cycle 28 Day 1)
- Administer study drug from subject supply in the office
- Study drug disposition (unless this is the last visit of the extension study)
- Assess AEs
- Assess Concomitant medication usage/confirmation. If pain medications are taken, list name, dosage, frequency, etc.
- Assess compliance by pill count

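### PSA-only progressors may stay on study under the Synopsis but can be ended under Section 8.2 and the no-PD gates, with no later scans for the radiographic endpoints

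*Combined protocol and SAP*

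**What the plan says.** **Definition and permission (Synopsis, Study Design).** Progression is assessed clinically, by PSA every 4 weeks, and by imaging every 12 weeks. "Progressive disease will be considered on the occurrence of the first assessed progression event". The next sentence adds: "For subjects with PSA progression may continue on study drug until radiographic and/or clinical progression", at the Investigator's discretion and with Medical Monitor agreement.

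**Dosing rule (Section 8.2).** Disease is re-evaluated every 3 cycles. A PSA rise on its own is one of the listed examples of a mixed response. Treatment can then run 4–6 weeks longer, after which "another PSA or tumor assessment can be scheduled to confirm if disease progression is determined. In case PD is confirmed that will conclude" (an end-of-study visit follows).

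**Gates to further cycles.**
- Synopsis, Duration of study: "subjects without progressive disease (PD) may continue GT0918 treatment with the approval of the investigator and sponsor". The same sentence goes on: "treatment can continue until a subject experience an intolerable adverse event (AE) or bone or radiographic disease progression".
- Section 6.1 makes continuation conditional on "no progressive disease, no intolerable adverse event, no radiographic disease progression".
- Section 6.2: "Eligible subjects (without PD) have the option to be treated for additional up to 24 cycles at their assigned dose level until PD".
- Section 8.2 repeats the no-PD condition at the end of cycles 6, 12, 18 and 24.
- Section 9.2.3: "Eligible subjects (no disease progression) have the option to continue additional cycles".
- Schedule of Assessments, footnote 12, also requires no disease progression.

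**Leaving the study.** Section 7.3 lists PD among the reasons for withdrawal, and Section 7.4 rules out re-entry. The end-of-study list (Section 9.2.4) and the end-of-study and safety follow-up columns of the schedule contain no imaging.

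**Endpoints.** rPFS and time to radiographic progression are secondary objectives (Section 4.2). Radiographic progression at 6 and 12 months is a secondary endpoint (Section 5.2).

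**The concern.** Under the Synopsis definition, a subject whose only event is PSA progression has PD. One sentence later he may stay on drug. Section 8.2 can be read to end his participation once a repeat PSA confirms PD, and the gates shut out anyone with PD without saying whether PSA-only PD counts. No sentence says which rule governs.

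This matters because scans are tied to staying on treatment. A subject stopped on PSA alone leaves with no scheduled scan at or after exit. Whether radiographic follow-up exists then depends on PSA, which is plausibly related to the risk of radiographic progression, so censoring at the last scan is likely to be informative. Section 13.4 gives no rPFS definition or censoring rule. The SAP promised in Section 13 can supply one, but it cannot recover scans that were never done.

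**Working it through.** The plan states no figure on this point, so there is none to reproduce. The check compares the rules and then counts scans.

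**1. The rules applied to one subject: PSA progression, no radiographic or clinical progression**

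| Place | Result for this subject |
|---|---|
| Synopsis, Study Design | Has PD; may continue with Medical Monitor agreement |
| Section 8.2, mixed response | 4–6 more weeks, then PSA or tumor assessment; confirmed PD ends the study |
| Synopsis, Duration of study: gate | Not admitted, if PD includes PSA |
| Synopsis, Duration of study: stop rule | Continues: only bone or radiographic progression stops treatment |
| Sections 6.1, 6.2, 8.2 gates | Not admitted, if PD includes PSA |
| Section 9.2.3 and footnote 12 | Not admitted, if progression includes PSA |

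Section 6.1 lists PD separately from radiographic progression, so PD there cannot be assumed to mean imaging only. The Duration of study paragraph points both ways, and its stop rule omits the clinical progression named under Study Design. Footnote 3 also requires that progression be ruled out before further cycles, but it belongs to the imaging row and most naturally means radiographic progression. I do not count it as a conflict.

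**2. Scheduled scans.** With 28-day cycles, Cycle c Day d falls on study day 28(c − 1) + d. The post-baseline scans in Sections 9.2.2 and 9.2.3 fall on days 85, 169, 253, 337, 421, 505, 589, 672, 756 and 840: 10 scans at nominal days, ignoring visit windows.

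**3. Exit through Section 8.2.** Day 85 scan without PD, PSA rising. The repeat PSA falls between 85 + 28 = Day 113 and 85 + 42 = Day 127. If PD is confirmed on PSA, the last scan is Day 85 and 9 of 10 are lost, including Day 169 (6 months). If the site chooses a tumor assessment instead, one extra scan exists at exit.

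**4. Refusal at a gate**

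| Gate | Day | Scans kept | Scans lost |
|---|---|---|---|
| C7D1 | 169 | 2 | 8 |
| C13D1 | 337 | 4 | 6 |
| C19D1 | 505 | 6 | 4 |
| C25D1 | 673 | 8 | 2 |

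Refusal at C7D1 removes Days 253 and 337, so that subject has no radiographic status near 12 months. If the Synopsis permission is applied, these scans are done.

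**5. Illustration of bias; every input is assumed.** Let f be the share of PSA-only progressors among those free of radiographic PD after Day 85, d their excess risk of radiographic PD by Day 169, s the share of them stopped and censored at Day 85, and p0 the risk in the others. Assume that stopped and kept PSA-only progressors have the same risk.

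- True interval risk: p0 + f·d
- Estimate after censoring: p0 + d·f(1 − s)/(1 − f·s)
- Understatement: d·[f − f(1 − s)/(1 − f·s)]

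With f from 0.10 to 0.30 and d from 0.10 to 0.40:
- s = 1: 0.10 × 0.10 = 1.0 point, to 0.30 × 0.40 = 12.0 points.
- s = 0.5: (0.10 − 0.0526) × 0.10 = 0.5 point, to (0.30 − 0.1765) × 0.40 = 4.9 points.

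For scale, an assumed proportion of 30% in 30 subjects has standard error √(0.30 × 0.70/30) = 8.4 points, a 95% half-width of about 16 points.

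**The case against.** The best defence is that the text can be read coherently. The Study Design paragraph is the only place that says in terms what may happen after PSA progression, and it lets the subject continue. The Duration of study paragraph joins its no-PD gate to a stop rule of bone or radiographic progression, which implies that PSA alone does not end treatment. Sections 7.3 and 8.2 are permissive about withdrawal and about the repeat assessment. Continuation after PSA progression needs Medical Monitor agreement, the six-cycle decisions involve the Medical Monitor and/or sponsor, and Section 7.4 asks sites to discuss alternatives when a subject withdraws.

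Much of this stands, and it rules out several stronger readings:
- **A second PSA must end participation.** Section 8.2 offers PSA or tumor assessment after a list that mixes PSA and imaging examples. It speaks of a rising PSA, and the protocol has no numeric on-study rule for PSA progression. Exit at Day 113–127 is one possible reading, not a stated rule.
- **Sites act without coordination.** Medical Monitor and sponsor involvement limits that.
- **rPFS is biased by up to 12 points.** That figure takes both assumed maxima and supposes that every PSA-only progressor is stopped, so the Synopsis permission is never used.

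The defence does not remove the ambiguity. No sentence gives the Study Design permission priority over Section 8.2 or the gates, and discretion to continue does not say how a no-PD gate applies to someone whom the Synopsis counts as having PD. Nor does it supply a scan after exit.

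**Conclusion.** The point holds as an inconsistency with a specific consequence. The Synopsis permits PSA-only progressors to continue, while Section 8.2 and the gates can be read to remove them. Those removed have no scheduled imaging at exit or later, so scan loss can depend on PSA.

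The exposed quantities are secondary: rPFS, time to radiographic progression, and radiographic progression at 6 and 12 months. A reader might infer that dose selection is undermined, but the primary safety/RP2D objective does not use these scans. A reader might also infer a biased dose comparison. Both arms share the rules, and Section 13.1 gives no power or effect size for a comparison, so the main risk is to the absolute estimates.

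The scan counts follow from the schedule. The number of subjects affected and the size and direction of any bias do not: the documents give no PSA-progression rate and no link between PSA and radiographic risk. The figures of 1 to 12 points (all stopped) and 0.5 to 4.9 points (half stopped) only illustrate assumed inputs.

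**What to change.** 1. In Section 8.2 and at each gate (Synopsis Duration of study; Sections 6.1, 6.2, 8.2, 9.2.3; footnote 12), state that PSA progression alone is not PD for ending study participation or for entry to further cycles. PSA-only progressors who continue with Medical Monitor agreement then keep the existing 12-week scans until radiographic or clinical progression.
2. Add clinical progression to the stopping events in the Synopsis Duration of study paragraph.
3. Record PSA, radiographic and clinical progression as separate dated events, and state that PSA progression alone is not an rPFS event.
4. In the SAP, report the number of subjects stopped for PSA alone, by arm, and add a sensitivity analysis for their censoring.

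**Cost.** Protocol, data-collection and SAP wording, with no new visit or scan type. Some subjects stay on drug longer, which the Synopsis already permits under the same safeguard.

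**Limits.** Continuation remains discretionary, so subjects whom the Investigator still stops for PSA alone will lack later scans; item 4 shows the extent of that loss but does not repair it. First enrolment was planned for 2Q2019 and Version 5.0 is dated 18 March 2021, so scans missed before an amendment cannot be recovered.
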